Proportion of SARS-CoV-2 viral load BLQ/not detected or not detected at Day 7 assessed by RT-qPCR from NP samples: In the mFAS-NP, the proportion of participants with viral load BLQ/not detected or not detected at Day 7 assessed by RT-qPCR from NP samples.

SARS-CoV-2 viral load AUC assessed by RT-qPCR from saliva samples through Day 29: Defined as AUC of SARS-CoV-2 viral load from baseline through Day 29 from saliva samples at Days 3, 5, 7, 11, 14, 21, and 29. AUC is calculated using the trapezoidal method.

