Visit windowing rules: Assessments collected on the nominal visits per the protocol schedule will be included in by-visit summaries and analysis. If an assessment is missing from a nominal visit, available assessments from the unscheduled visits within the protocol-defined target-study-day range may be mapped to the corresponding nominal visit. The assessment occurring closest to the target study day will be used. If there are multiple assessments equally distant to the target study day, the earliest assessment will be used.

All diary data will be summarized based on the actual day.

Incomplete/missing data:

Imputation rules for missing dates of prior/concomitant medications, including COVID-19 vaccinations and prohibited medications, and procedures are provided in [Appendix C](#).

Imputation rules for missing AE are provided in [Appendix D](#).

Data that are continuous in nature but are reported in the form $< x$, $> x$, $\leq x$, or $\geq x$ (where x is considered as the limit of quantitation) will be set to limit of quantitation value with the following exceptions:

- For viral load data:
 - Viral load values reported as detected but BLQ of the PCR assay (<714 copies/mL) are imputed with half of LLOQ of the PCR assay (ie, 357 copies/mL)
 - Viral load values reported as not detected are imputed with 1 copy/mL (ie, $0 \log_{10}$ copies/mL)
 - All viral load analyses will use both observed and imputed viral load data. Listings present both observed and imputed viral load.
- For PK concentrations
 - Serum concentrations that are BLQ will be treated as zero for PK analyses, except for BLQ values observed between 2 quantifiable concentrations, which will be set to missing. If consecutive BLQ concentrations are followed by quantifiable concentrations in the terminal phase, those concentrations after BLQ concentrations will be treated as missing. Missing concentrations will be treated as missing in the PK parameter calculations.
- Efficacy endpoint data will be imputed as detailed in Section [5.5](#).
- Other incomplete/missing data will not be imputed, unless specified otherwise.

Treatment groups: The following treatment groups will be used for summary purposes:
ADG20, Placebo

All analyses and data summaries/displays for efficacy will be provided by treatment group using the appropriate analysis population unless otherwise specified.

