4.5.4. Modified Full Analysis Set-PCR

Modified Full Analysis Set-PCR (mFAS-PCR): will include all randomized participants with a positive baseline quantitative SARS-CoV-2 RT-PCR based on either an NP swab or saliva sample and who received study drug. Participants will be analyzed based on the treatment they are randomized to, irrespective of what treatment was actually received.

Two sub-populations of the mFAS-PCR will be defined:

- **mFAS-NP:** will utilize the baseline NP swab to determine a positive SARS-CoV-2 PCR
- **mFAS-S:** will utilize the baseline saliva sample to determine a positive SARS-CoV-2 PCR.

mFAS-non-Omicron-PCR: is the subset of the mFAS-non-Omicron with a positive baseline SARS-CoV-2 RT-PCR. The subpopulations mFAS-non-Omicron-NP and mFAS-non-Omicron-S based on sample type used to determine a positive SARS-CoV-2 PCR (as defined above) will also be analyzed.

mFAS-Omicron-PCR: is the subset of the mFAS-Omicron with a positive baseline SARS-CoV-2 RT-PCR. The subpopulations mFAS-Omicron-NP and mFAS-Omicron-S based on sample type used to determine a positive SARS-CoV-2 PCR (as defined above) will also be analyzed.

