Change from baseline in SARS-CoV-2 viral load (\log_{10} copies/mL) to Days 3, 5, 7, 11, 14, 21, and 29 assessed by RT-qPCR from saliva samples	Observed saliva baseline and post-baseline values are used to calculate change from baseline. Mixed model for repeated measures with treatment group and the prognostic factors (with observed saliva baseline) in the primary efficacy endpoint analysis as covariates. The LS mean for the point estimate in each group and 95% CIs will be presented. The difference in LS means between the ADG20 group and the placebo group and the 95% CIs for the differences will be determined. A plot of the LS means with 95% CIs by Day assessed by treatment group will be presented. The analysis will be performed on the mFAS-Non-Omicron-S with available data at each timepoint. In addition, a two-sample t-test will be used to compare change from baseline viral load between treatment at each time point without covariate adjustment (unadjusted mean difference).
SARS-CoV-2 viral clearance (Days 3, 5, 7, 11, 14, 21, and 29) assessed by RT-qPCR from saliva samples (and BLQ/not detected or not detected for NP sample for Day 7)	
In the mFAS-non-Omicron-S, the cumulative proportion of participants with viral clearance will be presented for each post-baseline time point. In the mFAS-non-Omicron-NP, the proportion of participants with viral load BLQ/not detected or not detected at Day 7 will be presented. The ADG20 arm will be compared to placebo using the analysis procedure outlined for the primary efficacy outcome.
 
In addition, these analyses will be presented for the subgroups of participants with observed baseline NP viral load >5 and $\leq 5 \log_{10}$ copies/mL.

Endpoint	Statistical Analysis Methods

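### The Day 7 NP 'BLQ/not detected' clearance analysis does not require a quantifiable baseline, so participants already below 714 copies/mL may count as cleared and dilute the difference

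*SAP*

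**What the plan says.** Four rules in the SAP meet here.

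- **Entry.** SAP 4.5.4 builds the PCR sets from "all randomized participants with a positive baseline quantitative SARS-CoV-2 RT-PCR based on either an NP swab or saliva sample" and, for the NP sub-population, "will utilize the baseline NP swab to determine a positive SARS-CoV-2 PCR". It sets no minimum load and does not say what makes a quantitative PCR positive.
- **Result categories.** SAP 4.1 separates two low results: "Viral load values reported as detected but BLQ of the PCR assay (<714 copies/mL) are imputed with half of LLOQ of the PCR assay", and "Viral load values reported as not detected are imputed with 1 copy/mL".
- **Response.** SAP 3.5.2 defines the endpoint as "the proportion of participants with viral load BLQ/not detected or not detected at Day 7 assessed by RT-qPCR from NP samples". That is the state at Day 7 alone, at two cut-offs. SAP Table 4 repeats it for the non-Omicron NP set: "In the mFAS-non-Omicron-NP, the proportion of participants with viral load BLQ/not detected or not detected at Day 7 will be presented". In Protocol Table 7-2 the row label names both cut-offs, but the method text names only the wider one.
- **Analysis.** Table 4 applies the primary method, whose covariates include continuous baseline NP viral load. It adds subgroups above and at or below 5 log10 copies/mL at baseline. SAP 5.5.4 describes these results as descriptive, without multiplicity control.

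**The concern.** A positive-baseline set suits the not detected version, because everyone starts outside the response category. The BLQ/not detected version widens the response category to everything below 714 copies/mL but keeps the same entry rule. If detected-but-BLQ counts as positive, some participants already satisfy the response definition before dosing, and those who stay there are reported under viral clearance.

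Such participants say almost nothing about whether ADG20 clears virus. They raise the clearance rate in both arms and pull the absolute difference and the ratio toward no effect. All of them fall in the subgroup at or below 5 log10, so the dilution is greatest there. The undefined term is a second problem: two programmers could build different NP sets from the same text.

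**Working it through.** **1. The plan's own figure.** Half of the limit is 714/2 = 357 copies/mL, the SAP's imputed value. On the log scale, log10(714) = 2.85 and log10(357) = 2.55. Both are below 5, so every baseline-BLQ participant is in the lower subgroup and none is in the upper one.

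**2. Direction.** Let f be the share BLQ at baseline, s the proportion of those still BLQ or not detected at Day 7, and p the response rate among participants quantifiable at baseline.

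Rate in an arm = f·s + (1 − f)·p

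If f and s are the same in both arms, the difference (ADG20 minus placebo) is (1 − f)(p1 − p0). It shrinks by the factor (1 − f) whatever the value of s.

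**3. Illustration.** Assume p0 = 20%, p1 = 35% and s = 1. The undiluted difference is 15.0 points and the ratio 1.75.

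| f | Placebo | ADG20 | Difference | Ratio |
|---|---|---|---|---|
| 2% | 21.6% | 36.3% | 14.7 | 1.68 |
| 5% | 24.0% | 38.2% | 14.2 | 1.59 |
| 10% | 28.0% | 41.5% | 13.5 | 1.48 |
| 20% | 36.0% | 48.0% | 12.0 | 1.33 |

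At f = 0 nothing changes.

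**4. A plausible f.** The documents give no baseline NP distribution and no detection limit. Assume log10 load is normal with mean μ (5.5 to 7) and SD σ (1.5 to 2), truncated at an assumed detection limit of 1.5 log10.

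f overall = [Φ((2.85 − μ)/σ) − Φ((1.5 − μ)/σ)] / [1 − Φ((1.5 − μ)/σ)]

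For the lower subgroup, the denominator becomes Φ((5 − μ)/σ) − Φ((1.5 − μ)/σ).

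With μ = 5.5 and σ = 2, f overall is (0.0929 − 0.0228)/0.9772 = 7.2%. In the lower subgroup it is 0.0702/(0.4013 − 0.0228) = 18.5%.

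| μ, σ | f overall | f at or below 5 log10 |
|---|---|---|
| 5.5, 2 | 7.2% | 18.5% |
| 6, 2 | 4.6% | 15.4% |
| 6, 1.5 | 1.7% | 6.6% |
| 7, 1.5 | 0.3% | 3.0% |

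**5. Size.** At the top of the range, a 15-point difference becomes 15 × (1 − 0.072) = 13.9 overall and 15 × (1 − 0.185) = 12.2 in the lower subgroup.

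**6. Effect on the test.** Without covariates, at f = 10% and an assumed 150 per arm, power is 69% in the whole set and 79% in the 135 per arm quantifiable at baseline. The planned model, however, adjusts for baseline viral load. I simulated the standardized risk difference with baseline load as the only covariate: μ = 5.5, σ = 2, 150 per arm, mean falls of 2.0 and 2.8 log10 with SD 1.2, and assay SD 0.5, all assumed.

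| | Difference, planned set | Difference, baseline ≥714 | Power, planned set | Power, baseline ≥714 |
|---|---|---|---|---|
| Overall | 13.5 | 14.3 | 91% | 90% |
| At or below 5 log10 | 13.2 | 15.6 | 53% | 51% |

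The estimate moves but the power does not. Once baseline load is in the model, near-certain responders add little variance, so the difference and its standard error shrink together.

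**The case against.** The strongest reply is that the premise is inferred. SAP 4.5.4 never says that a detected-but-BLQ result is positive, and the imputation rule in SAP 4.1 covers any visit; it shows that the category exists, not that it qualifies for the NP set. This stands. Inclusion is the natural reading, but the sponsor may intend otherwise, and then f is zero.

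A reader might also infer that these participants are automatic responders. They are not. Someone BLQ at baseline with a quantifiable Day 7 value is a non-responder; under the distributions above with no true change and assay SD 0.5, 19-27% fall in that group. Nor should the problem be sized by counting everyone who would be below 714 at Day 7 with no true change (0.4-8% overall, 5-20% in the lower subgroup). Of those, 26-53% were quantifiable at baseline, drifted below by assay noise, and would be kept by any baseline filter.

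The plan already contains much of the remedy: the not detected version, the subgroup above 5 log10, the baseline covariate, and separate Day 7 NP analyses of change from baseline and of load above 5 and 4 log10. These limit the consequence. They do not remove the dilution from the overall estimate, because the standardized difference averages over every participant in the set, or from the lower subgroup.

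Finally, the proportion below the limit at Day 7 is a legitimate state endpoint, and a baseline filter gives the two versions different denominators. That is true, but the SAP places the endpoint under viral clearance, and clearance implies starting above the limit.

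**Conclusion.** The point holds as a small, conditional flaw in one version of a non-key, descriptive endpoint. If detected-but-BLQ counts as positive, both clearance rates are raised and the risk difference is diluted by about the baseline-BLQ share: 0.3-7% overall and 3-19% in the subgroup at or below 5 log10, under assumed distributions. On an assumed 15-point difference that is about 1 point overall and up to about 3 in the subgroup.

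Two stronger readings are not supported. It is not bias in favour of ADG20: entry is fixed before dosing and, under randomization, the expected effect is toward no difference. Nor would a real effect be made to look absent: the shrinkage is modest and power is nearly unchanged when baseline viral load is in the model. One condition applies. SAP 5.6 describes an age-only model for subgroup analyses, and Table 4 does not say whether it governs these subgroups. If it does, the unadjusted comparison in the working is the closer guide there.

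**What to change.** - In SAP 3.5.2 and Table 4, run the BLQ/not detected version, overall and in the subgroup at or below 5 log10, in mFAS-non-Omicron-NP participants with baseline NP load of at least 714 copies/mL.
- Keep the not detected version in the full NP set.
- In SAP 4.5.4, state whether a detected-but-BLQ baseline result is positive.
- Report the number BLQ at baseline by arm.

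The cost is a sentence or two, one filter on a pre-dose value, and a slightly smaller denominator for this one version. Because the filter uses only baseline data, the randomized comparison is preserved. SAP 3.2 has the SAP signed before unblinding, so the change belongs before that point.

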5.5. Efficacy Analyses

5.5.1. Primary Efficacy Analysis

The primary efficacy endpoint is the incidence of COVID-19-related hospitalization or all-cause death through Day 29 in the mFAS-non-Omicron analysis set. The null and alternative hypotheses are the following:

$$H_0: P_1 - P_0 = 0$$

$$H_1: P_1 - P_0 \neq 0$$

P_1 and P_0 are the proportion of participants with COVID-19-related hospitalization or all-cause death through Day 29 in the ADG20 and placebo groups respectively. Using the methodology as described below (with additional details in [Appendix J](#)), a standardized estimator for a binary outcome (standardized risk difference/standardized relative risk reduction) will be estimated with adjustment for the following prognostic factors: age (continuous), sex (categorical), baseline qualitative serostatus (categorical: positive, negative), BMI (continuous), and baseline viral load from NP sample (continuous as \log_{10} copies/mL). For all efficacy analysis models, missing baseline serostatus will be imputed as positive and missing baseline BMI and viral load will be imputed as the average of all participants with non-missing data at baseline. Age is a randomization stratification factor and, thus, cannot be missing.

[Appendix I](#) summarizes the main estimation and sensitivity analyses for the primary estimand (Estimand 1a). The main estimation for Estimand 1a will use available data for COVID-19 hospitalization or all-cause death through Day 29, implemented in the mFAS-non-Omicron analysis set. Missing status on COVID-19-related hospitalization or all-cause death will be imputed as not having a COVID-19 hospitalization or all-cause death. The number and percentages of participants who experience and do not experience a COVID-19-related hospitalization or all-cause death will be summarized by treatment group, including summaries of missing data, COVID-19-related hospitalizations, and all-cause death. The observed risk difference (placebo minus ADG20) with 95% CI (using the Miettinen-Nurminen method), observed relative risk reduction, standardized risk difference with 95% CI and associated p-values, and standardized relative risk reduction with 95% CI will be provided.

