Change from baseline in SARS-CoV-2 viral load (\log_{10} copies/mL) to Day 7 (± 1) assessed by RT-qPCR from NP samples	
Observed NP baseline and post-baseline values are used to calculate change from baseline. ANCOVA with treatment group and the prognostic factors (with observed NP baseline) as in the primary efficacy endpoint analysis as covariates. The LS mean for the point estimate in each group and 95% CIs will be presented. The difference in LS means between the ADG20 group and the placebo group and 95% CIs for the differences will be determined. The analysis will be performed on the mFAS-non-Omicron-NP with available data at Day 7. In addition, two-sample t-test will be used to compare change from baseline viral load between treatment without covariate adjustment (unadjusted mean difference).
 
If Day 7 value is missing, the earliest measurement closest to the Day 7 visit within 1 day (including scheduled and unscheduled visit) will be used.

Viral load >5 (\log_{10} copies/mL) on Day 7 (± 1) based on NP samples	The methods for the primary efficacy endpoint will be used. Analysis will be performed on the mFAS-non-Omicron-NP with available data at Day 7. Analysis will be repeated using a second definition of high viral load (viral load $>4 \log_{10}$ copies/mL).
Duration of SARS-CoV-2 viral shedding from Day 1 through Day 29 assessed by RT-qPCR from saliva samples	KM methodology will be used to analyze duration of viral shedding from Day 1 through Day 29 of SARS-CoV-2 RNA. KM curves, the number and percentage of censored observations and the median, 25 th and 75 th percentiles will be provided. Survival distributions will be compared between ADG20 and placebo using a log rank test stratified by age (categorical) and baseline serostatus. A stratified Cox Proportional Hazard model will be used to estimate the hazard ratio where the model includes age (categorical as 12-17 years, 18-65 years and >65 years) as a stratification variable and sex (categorical), baseline serostatus (categorical as positive; negative), baseline BMI (continuous) and baseline viral load (continuous as \log_{10} copies/mL) as covariates. Comparison of the survival distributions will use the score test for the hazard ratio from this Cox model. Analyses will be performed on the mFAS-non-Omicron-S.

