SARS-CoV-2 viral load AUC (\log_{10} copies/mL) assessed by RT-qPCR from saliva samples through Day 29	An ANCOVA will be used to compare ADG20 and placebo where the prognostic factors in the primary efficacy endpoint analysis will be used as covariates. Participants in the mFAS-non-Omicron-S will be included in this analysis. The AUC from Day 1 through Day 29 will be calculated according to the linear trapezoidal rule using the measured SARS-CoV-2 viral load above the lower limit of quantification. No AUC values will be calculated when Day 1 and/or Day 29 values are missing, or if there are more than 3 values missing in the profile. In addition, two-sample t-test will be used to compare viral load AUC between treatment without covariate adjustment (unadjusted mean difference).

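### On the literal SAP text, saliva viral-load AUC and saliva clearance are adjusted for the nasopharyngeal (NP) baseline; the saliva baseline is available and likely more efficient

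*SAP*

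**What the plan says.** SAP 5.5.1 lists five prognostic factors for the primary model: age, sex, baseline qualitative serostatus, BMI and "baseline viral load from NP sample". It adds that, in all efficacy models, "missing baseline BMI and viral load will be imputed as the average of all participants with non-missing data at baseline".

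SAP 5.5.4, Table 4, then deals with the virologic endpoints row by row:

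- **NP change from baseline to Day 7:** "ANCOVA with treatment group and the prognostic factors (with observed NP baseline) as in the primary efficacy endpoint analysis as covariates".
- **Saliva change from baseline:** a repeated-measures model using "the prognostic factors (with observed saliva baseline) in the primary efficacy endpoint analysis as covariates".
- **Saliva clearance, with Day 7 NP clearance in the same row:** "The ADG20 arm will be compared to placebo using the analysis procedure outlined for the primary efficacy outcome". No specimen is named.
- **Saliva AUC through Day 29:** an ANCOVA "where the prognostic factors in the primary efficacy endpoint analysis will be used as covariates". No specimen is named.
- **Duration of saliva shedding:** a Cox model with baseline viral load as a covariate. No specimen is named.

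The AUC row also says "No AUC values will be calculated when Day 1 and/or Day 29 values are missing". Protocol 7.8 has the same pattern. Protocol 7.6 does not name the specimen, so the NP definition comes from the SAP.

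**The concern.** Two change-from-baseline rows match the baseline specimen to the outcome specimen. The saliva AUC row and the saliva part of the clearance row do not, and by cross-reference they take the NP value. No reason is given.

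The saliva baseline looks like the better covariate for two reasons. First, the AUC runs from Day 1 without baseline subtraction, so a participant who starts high in saliva will tend to have a high AUC whatever the treatment. Second, the saliva value is available for everyone analysed. The saliva set requires a positive baseline saliva PCR (SAP 4.5.4), and no AUC is calculated without a Day 1 value. The NP value can be missing and then mean-imputed, or not detected and then set to 0 log10 (SAP 4.1).

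What is at stake is the width of the confidence intervals for secondary antiviral endpoints, in a trial whose primary efficacy population is about 320 instead of the planned 1084. In the shedding model, an unnamed specimen also leaves the choice to the programmer.

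**Working it through.** **Is there a figure to reproduce?** No. The documents give no SD, correlation, power or precision for any saliva endpoint. The text settles which covariate is used; the size of the effect can only be shown over a range of assumptions.

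**Which covariate applies.** AUC row → primary prognostic factors → SAP 5.5.1 → NP sample. Clearance row → primary procedure → SAP 5.5.1 → NP sample. For Day 7 NP clearance that is the matched specimen; for saliva clearance it is not.

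**AUC.** Let *rs* be the correlation of saliva baseline with saliva AUC, and *c* the correlation of NP baseline with saliva baseline. Assume that NP carries no information on the AUC beyond what saliva carries, so the NP–AUC correlation is *rs·c*. This is unfavourable to NP. ANCOVA residual variance is proportional to 1 − r², so the relative efficiency of NP against saliva adjustment is

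RE = (1 − rs²) / (1 − rs²c²), and precision lost = 1 − RE.

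Example with *rs* = 0.5 and *c* = 0.5: RE = 0.75 / 0.9375 = 0.80, a 20% loss, with a confidence interval wider by a factor of 1/√0.80 = 1.12.

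Precision lost (%):

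| rs | c = 0.3 | c = 0.5 | c = 0.7 | c = 0.9 |
|---|---|---|---|---|
| 0.2 | 3.7 | 3.0 | 2.1 | 0.8 |
| 0.3 | 8.3 | 6.9 | 4.8 | 1.8 |
| 0.5 | 23.3 | 20.0 | 14.5 | 6.0 |
| 0.7 | 46.6 | 41.9 | 32.9 | 15.4 |
| 0.8 | 61.8 | 57.1 | 47.6 | 25.2 |

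The loss passes one half only when rs² > 0.5 / (1 − 0.5c²). That means *rs* above 0.72, 0.76, 0.81 or 0.92 for *c* = 0.3, 0.5, 0.7 or 0.9.

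A different quantity is the share of the viral-load covariate's own variance reduction that is lost, 1 − c². It is 91% at *c* = 0.3, 75% at 0.5, 51% at 0.7 and 19% at 0.9, so it exceeds half when *c* is below √0.5 = 0.71.

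**How directly the baseline enters the AUC.** Under the trapezoidal rule with visits at Days 1 and 3, the Day 1 value has weight (3 − 1)/2 = 1 day out of 28. Its direct contribution is small. A large *rs* would have to come from persistence of the starting level over later days, which the documents do not quantify.

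**Clearance.** The standardised risk difference from the logistic model was simulated with 320 participants (the size of the saliva-positive subset is not stated), 1:1 allocation, about 50% clearance and 1,500 replicates. The log-odds slope per SD of saliva baseline was assumed. RE of NP against saliva adjustment:

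| Slope | c = 0.3 | c = 0.5 | c = 0.7 |
|---|---|---|---|
| 0.5 | 0.927 | 0.952 | 0.977 |
| 1.0 | 0.854 | 0.877 | 0.906 |
| 1.5 | 0.710 | 0.780 | 0.798 |

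The loss runs from 1 − 0.977 = 2% to 1 − 0.710 = 29%.

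**The case against.** The strongest reply is that little depends on this. SAP 5.5.4 calls these analyses descriptive, and they lie outside the testing hierarchy. The AUC also has an unadjusted t-test, and the saliva repeated-measures model analyses the same samples with the matched baseline. All of that stands, and it limits the weight of the point.

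The reply can also say that the size is unknown. If NP and saliva loads agree closely, or if NP carries information of its own, little is lost; at *c* = 0.9 and *rs* = 0.5 the loss is 6%. That stands too.

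A third argument concerns intent. The change-from-baseline rows may name a specimen only because the outcome is a change from that specimen, or to stress observed over mean-imputed values. The NP row carries the parenthesis although NP is already the primary covariate. So the saliva parenthesis does not prove that the sponsor saw the need and then overlooked it elsewhere. It shows only that the rows differ without explanation.

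Two stronger readings are tempting. A reader might infer that the plan throws away most of the available precision. The documents contain nothing to support that: for AUC it happens only in one corner of the assumed range (*rs* = 0.8 with *c* of 0.5 or less in the table), and for clearance in none of the simulated settings. A reader might also infer bias, because the saliva set is chosen by saliva positivity and not by randomisation. The Day 1 saliva sample is taken before dosing (protocol 6.2), so selecting on it leaves the randomised comparison intact.

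**Conclusion.** The mismatch is real on the literal text and is confined to the saliva AUC ANCOVA and the saliva part of the clearance analysis. The shedding Cox model has the lesser fault of leaving the specimen open. Either pre-dose baseline gives a valid comparison. The NP baseline is likely the less efficient choice for a saliva outcome, by about 1% to 62% of precision for AUC and about 2% to 29% for clearance. Both ranges rest wholly on assumed correlations and slopes, and the AUC range also assumes that NP adds nothing beyond saliva. No claim of bias, of type I error inflation or of a loss of most of the precision is supported.

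**What to change.** In SAP Table 4:

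1. Saliva AUC row: after the reference to the prognostic factors, add *(with observed saliva baseline viral load in place of NP)*.
2. Clearance row: add the same words for the saliva analyses only. Day 7 NP clearance keeps the NP baseline.
3. Saliva shedding row: state that the baseline viral load in the Cox model is the saliva value.

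Leave the NP baseline as it is in the primary and key secondary clinical models and in the NP virologic endpoints. If NP adjustment of the saliva endpoints is intended, say so and give the reason.

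The cost is a few words and a covariate swap in the code; the saliva baseline is already collected. SAP 3.2 requires the SAP to be final before unblinding, so the change belongs before that point. Made later, it should be labelled post hoc.
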